#### 6.1.5. Vital Signs

The analysis of vital signs will be approached in two ways.

Vital signs are to be measured at Screening, predose and at 1, 2, 4, 6, and 24 hours postdose on dosing Days 1, 15, predose at 1 and 6 hours postdose on Days 29, 64, 135, 183, and 279 and on Day 302/ET At each of these times, temperature, heart rate, respiratory rate, systolic and diastolic blood pressure, and pulse oximetry will be measured.

#### **Acute Effects After Dosing**

On each dosing day, the change in each vital sign from predose on that day to postdose (i.e., from predose to 1 hour postdose, to 2 hours postdose, etc.) will be calculated. Summaries of actual values and change from predose for each dosing day will be presented.

#### **Chronic Effects**

To examine for possible chronic effects, the change from baseline (the predose value on Day 1) to the predose value on later dosing days and to Day 302/ET will be determined. Summaries of actual values and change from baseline for subsequent dosing days (Days 15, 29, 64,135, 183, and 279) and for Day 302/ET will be presented.

Vital signs (temperature, pulse, systolic and diastolic blood pressure and pulse oximetry) will also be examined to determine the incidence of potentially clinically relevant abnormalities.

#### Shift analysis

Product: Nusinersen	Statistical Analysis Plan
Study: 232SM203	Version: 1.0

The number of subjects evaluated and the number of subjects with potentially clinically relevant abnormalities will be presented. All post baseline data will be used to identify abnormalities, regardless of whether a scheduled or unscheduled visit. The criteria for potentially clinically relevant postdose abnormalities are shown in Table 6 below:

Vital Sign	Criteria for Abnormalities
Temperature	<36°C
	>38°C
Pulse	<60 bpm
	>100 bpm
Systolic Blood Pressure	<90 mmHg
	>140 mmHg
	>160 mmHg
Diastolic Blood Pressure	<50 mmHg
	>90 mmHg
	>100 mmHg
Weight	7% or more decrease from baseline
	7% or more increase from baseline
Respiratory Rate	<12 breaths/min
	>20 breaths/min

#### 6.1.6. Growth parameters

Growth parameters include weight for age, and ulnar length.

The growth parameters are to be assessed during screening, on dosing days (Days 1, 15, 29, 64, 135, 183 and 279) and on Day 302/ET.

The 2000 CDC Growth Charts (ages 2 to <20 years) will be used to assess the weight change for older subjects. The National Center for Health Statistics provides a SAS macro which can be downloaded from their website [https://www.cdc.gov/growthcharts/clinicalcharts.htm] and this will be utilized to calculate the weight for age percentiles for each participant in the later onset population.

Product: Nusinersen	Statistical Analysis Plan
Study: 232SM203	Version: 1.0

Summary statistics for actual values and change from baseline in each growth parameter will be presented by treatment group and visit.

Baseline growth parameters will be summarized and also the frequency and percentage for weight and height for age will also be presented for each of in the following categories:  $\leq 1$  st,  $\leq 3$  rd,  $\leq 5$  th,  $\leq 15$  th,  $\leq 25$  th,  $\leq 50$  th and > 50 th percentile.

[figure not shown]

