### 7.1.7. Growth parameters

Growth parameters include length for age, weight for age, weight for length, head circumference for age, chest circumference, head to chest circumference ratio, and arm circumference.

The growth parameters are to be assessed during screening, on dosing days (Days 1, 15, 29, 64, 135, 183 and 279) and on Day 302/ET.

The weight for age and length for age will be summarized using the WHO child growth standards (WHO Child Growth Standards, 2006) for subjects aged up to 5 years and similarly the WHO growth reference data (WHO, 2007) for older subjects. These standards comprise percentiles for weight and length for age by sex and are available on a website (www.who.int) in txt files. Subjects will be cross referenced with these files, given the age and sex of the subject to determine below which percentile they lie for each parameter.

Summary statistics for actual values and change from baseline in each growth parameter will be presented by treatment group and visit.

Baseline growth parameters will be summarized and also the frequency and percentage for weight and length for age will also be presented for each of in the following categories:  $\leq 1$  st,  $\leq 3$  rd,  $\leq 5$  th,  $\leq 15$  th,  $\leq 25$  th,  $\leq 50$  th and > 50 th percentile.

[figure not shown]
Product: Nusinersen	Statistical Analysis Plan
Study: 232SM203	Version: 3.0 Final

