#### **Secondary Safety Objectives**

To examine the safety and tolerability of nusinersen administered intrathecally at higher doses to participants with SMA.

Secondary Safety Endpoints

- Incidence of AEs, including SAEs
- Shifts from baseline in clinical laboratory parameters, ECGs, and vital signs
- Change in growth parameters
- Shifts from baseline in coagulation parameters (aPTT, PT, and INR)
- Change in urine total protein
- Change from baseline in neurological examination outcomes
- The proportion of participants with a post baseline platelet count below the lower limit of normal on at least 2 consecutive measurements
- The proportion of participants with a post baseline QTcF of > 500 msec and an increase from baseline to any post baseline timepoint in QTcF of > 60 msec

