# 4.4. General Principles

Descriptive summary statistics will be presented for all endpoints collected. Unless otherwise specified, for continuous endpoints, the summary statistics will generally include number of participants with data, mean, standard deviation, median, 25th percentile, 75th percentile, minimum and maximum. For categorical endpoints, the summary statistics will generally include number of participants with data, and the percentage of those with data in each category.

All summaries and listings will be presented by study groups unless otherwise specified. Visits in listings will be displayed as per CRF data collection rather than analysis visits.

The statistical software, SAS®(Version 9.4) will be used for all summaries and statistical analyses.

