# 5.7.6. Growth parameters

Growth parameters for infantile-onset and later-onset SMA population include weight, height/length ulnar length, length for age (<18 years of age) and weight for age (<18 years of age).

The growth parameters are to be assessed during screening, on dosing days (Days 1, 121, and 241) and on Day 302/ET.

The 2000 CDC Growth Charts (ages 2 to <20 years) will be used to assess the weight change for older subjects. The National Center for Health Statistics provides a SAS macro which can be downloaded from their website [https://www.cdc.gov/growthcharts/clinical\_ charts.htm] and this will be utilized to calculate the weight for age percentiles for each participant in the later onset population.

Subjects will be cross referenced with these files, given the age and sex of the subject to determine below which percentile they lie for each parameter.

For patients <18 years of age the weight and length for age percentiles will be determined and summarized over time.

Summary statistics for actual values and change from baseline in each growth parameter will be presented by visit.

Baseline growth parameters for subjects <18 years of age at baseline, will be summarized and also the frequency and percentage for weight and height for age will also be presented for each of in the following categories:  $\leq 1$  st,  $\leq 3$  rd,  $\leq 5$  th,  $\leq 15$  th,  $\leq 25$  th,  $\leq 50$  th and > 50 th percentile.

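### Part B later-onset SAP: change in weight for age is summarised in percentile points, which shrink losses in underweight children and can give the mean change the wrong sign

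*SAP*

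**What the plan says.** The Part B later-onset SAP lists "Change in growth parameters" among its secondary safety endpoints. Section 6.1.6 says: "Growth parameters include weight for age, and ulnar length". Weight is converted with the CDC 2000 charts, by a macro to be "utilized to calculate the weight for age percentiles for each participant in the later onset population". The section continues: "Summary statistics for actual values and change from baseline in each growth parameter will be presented by treatment group and visit". Under Section 4.4, a continuous summary generally gives "mean, standard deviation, median, 25th percentile, 75th percentile, minimum and maximum".

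The percentile-band table, which runs from the 1st percentile or below to above the 50th, is worded for baseline: "Baseline growth parameters will be summarized and also the frequency and percentage for weight and height for age". Section 6.1.6 states no post-baseline shift between bands. Separately, the vital-signs table in Section 6.1.5 flags a weight decrease or increase of 7% or more from the child's own baseline.

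Related wording appears in two other parts. In Part B infantile-onset (Section 7.1.7), children are looked up in WHO files "to determine below which percentile they lie for each parameter". In Part C (Section 5.7.6): "For patients <18 years of age the weight and length for age percentiles will be determined and summarized over time". Neither section names a z-score.

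**The concern.** Percentile points are not an interval scale. The same loss relative to age and sex is a large number near the median and almost nothing in the lower tail. A mean of percentile changes therefore weights each child by starting position: children near the median dominate it, and underweight children, in whom further loss matters most, barely count.

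With up to 16 children in the 50/28 mg arm and up to 8 in the control arm (Section 2.1), a few mid-range children can settle the sign of an arm's mean. What is at stake is whether this safety summary can show how large a weight loss is in underweight children, and whether a comparison of arm means on it can be trusted.

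**Working it through.** The SAP states no figure on this point, so there is none to reproduce.

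**Inputs from the SAP.** Up to 16 and 8 children per arm (Section 2.1); percentile scale with change from baseline (6.1.6); the summary statistics (4.4); the 7% weight flag (6.1.5).

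**Assumed inputs, not in the SAP.** Baseline z of the children who fall, -3 to 0. The others start at z = -0.5, -0.25 or 0 and gain 1, 0.5 or 0.25 SD respectively.

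**Step 1: one child.** Percentile = 100·Φ(z), so a 1 SD fall changes it by 100·[Φ(z-1) - Φ(z)].

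| Baseline z | Percentile before | Percentile after | Change, points |
|---|---|---|---|
| 0 | 50.00 | 15.87 | -34.13 |
| -1 | 15.87 | 2.28 | -13.59 |
| -1.5 | 6.68 | 0.62 | -6.06 |
| -2 | 2.28 | 0.135 | -2.14 |
| -2.5 | 0.62 | 0.023 | -0.60 |
| -3 | 0.13 | 0.003 | -0.13 |

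By contrast, a gain from z = -0.5 to +0.5 adds 38.29 points.

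**Step 2: one arm of 16.** Let 12 children fall 1 SD and 4 rise from z = -0.5 to +0.5. The mean z change is (12 × -1 + 4 × 1)/16 = -0.50 wherever the fallers start. The mean percentile change is not constant:

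- fallers at z = -2: (12 × -2.14 + 4 × 38.29)/16 = +7.97
- fallers at z = -1: (12 × -13.59 + 4 × 38.29)/16 = -0.62
- fallers at z = 0: (12 × -34.13 + 4 × 38.29)/16 = -16.03

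In the first case the planned row would read mean +7.97, median -2.14, lower quartile -2.14, minimum -2.14, maximum +38.29.

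The gains need not be large. With 12 fallers at z = -2.5 and 4 children rising 0.2 SD from the median, the mean percentile change is (12 × -0.60 + 4 × 7.93)/16 = +1.53. The mean z change is (12 × -1 + 4 × 0.2)/16 = -0.70.

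**Step 3: how many can fall a full SD with the mean percentile change still positive?**

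| Arm size | Fallers' baseline z | Others +1 SD | Others +0.5 SD | Others +0.25 SD |
|---|---|---|---|---|
| 16 | -2 | 15 | 14 | 13 |
| 16 | -1.5 | 13 | 12 | 9 |
| 8 | -2 | 7 | 7 | 6 |
| 8 | -1.5 | 6 | 6 | 4 |

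**Step 4: the 7% decrease flag.** Assume the SD of log weight at a given age is s = 0.12 to 0.18, and expected log growth to Day 302 is g = 0.08 to 0.15. A child who falls 1 SD changes weight by exp(g - s) - 1. The extremes are exp(0.08 - 0.18) - 1 = -9.5% and exp(0.15 - 0.12) - 1 = +3.0%. On a 4 × 4 grid over these ranges, 13 of 16 combinations do not reach a 7% loss.

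**The case against.** A reader might infer that growth failure would be hidden. The SAP does not support that. It reports the median, quartiles, minimum and maximum as well as the mean. If more than half of an arm falls, the median change is negative, and a mean and median of opposite sign would be visible in the same row. This part of the objection stands. What it leaves is the size: a median of -2.14 points reads as negligible although it stands for a full SD.

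The 7% table also counts increases. On the growth assumed above, a child growing as expected gains exp(0.08) - 1 = 8.3% to exp(0.15) - 1 = 16.2% by Day 302 and would be flagged, while a child who fell 1 SD would not. A shortfall in that count is a real signal, but a crude one: it is not standardised for age and gives no size.

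The sign reversal is a constructed scenario. It weakens when the fallers start at z = -1 and is absent at z = 0. The low bands in the baseline table allow for underweight children but do not say how many there are.

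A reader might also extend the point to every part of the study. In Part A, growth parameters are only listed, so no mean percentile change is planned. Part C also summarises raw weight and height/length. The infantile-onset section also covers weight for length and head, chest and arm circumference, and its lookup wording does not clearly describe a mean percentile change.

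Finally, Section 6.1.6 says its parameters include the two named, and a figure directly after the band table is not reproduced in the public copy. The absence of other growth displays cannot be asserted. No hypothesis test rests on this summary, and an IDMC reviews unblinded safety data.

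**Conclusion.** The point holds for the Part B later-onset SAP. Change in weight for age is summarised on a scale where a 1 SD loss shrinks from 34.1 points at the median to 2.1 at z = -2 and 0.6 at z = -2.5. That compression is arithmetic and needs no assumption about the enrolled children beyond some being underweight.

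The wrong sign of the mean is conditional. It needs fallers starting at about z = -1.5 or lower and a few mid-range children who gain. The SAP neither states nor excludes this.

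The supported conclusion is that the size of a loss is understated and the mean can mislead. It is not that growth failure would go undetected, nor that all parts are equally affected. Part B infantile-onset and Part C share the percentile scale with less consequence, and Part A is not affected. This is an inexpensive improvement to a descriptive safety summary and does not threaten any efficacy conclusion.

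**What to change.** - **Part B later-onset, Section 6.1.6:** summarise actual value and change from baseline by arm and visit as age- and sex-standardised weight-for-age z-scores from the same CDC reference. Where an exact percentile is available, z is its inverse-normal transform. Keep percentiles for the baseline category table.
- **Optional in the same section:** add a count of children whose z-score falls by a prespecified amount, or a post-baseline shift table of the percentile bands, so that individual losses are visible.
- **Part B infantile-onset, Section 7.1.7, and Part C, Section 5.7.6:** use z-scores for the weight-for-age and length-for-age summaries. In Section 7.1.7, derive z from the reference itself and not from the band a child falls below, because a band cannot be converted back to an exact value.
- **Part A:** no change.

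The cost is a wording change and one derived variable per measure from reference data already in use. No new data are collected.

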#### 6.1.7. LP opening pressure

[figure not shown]
LP opening pressure will only be measured at Days 1, 15, and 279 to avoid potential unblinding. A lack of published data exists in terms of the variability of opening pressure between and within subjects. It is suspected that a simple change in position of a subject during the measurement or change of instrument used contributes to variability in the measurement.

[figure not shown]
The actual value and change from baseline to each visit will be summarized by treatment groups all the data collected will be listed.

# 6.1.8. X-ray Examination of Spine

[figure not shown]
The X-rays will be used to determine the severity of scoliosis by measuring the Cobb angle in the later-onset SMA subjects. The spine X-ray is performed at screening with the participant in a sitting or supported sitting position following an image acquisition guideline. Summary and listing of baseline Cobb angle will be presented.

Product: Nusinersen
Study: 232SM203

#### 9. Pharmacodynamic Endpoints

As detailed earlier NfL is defined as a secondary endpoint.

In addition, plasma and CSF PK

concentrations will be analyzed with plasma and CSF biomarkers to establish PK/PD correlation. PK/PD and exposure-response may also be conducted on efficacy. The results of this study may be combined with other nusinersen studies to perform population PK/PD analyses, including exposure-response analysis.

#### **10.** Other Analyses

Not applicable.

#### 11. Statistical Considerations for Interim Analysis

Not applicable

#### 12. Changes from Protocol-Specified Analyses

Added NF-L as a secondary endpoint.

#### **15. APPENDICES**

#### **APPENDIX A.**

#### i Seeds for MI

Table 9: Seeds used for each endpoint in MI for Later-Onset SMA population

Endpoint	Seed
HFMSE	25980495
RULM	47886416
NfL in plasma	7953683
NfL in CSF	4711630
PedsQL	12676424
ACEND	68757534

#### ii Adverse Events

In the situation where worsening in severity (including seriousness) occurs for an adverse event, study sites are instructed to enter an end date and start a new record for the adverse event. In the new record, the changed severity is to be recorded and the start date will be set to be the end date of the previous record. Data linking those records are collected in the data base. Consider three scenarios:

- The first AE record occurs prior to the first dose, the second AE record occurs on or after the first dose, and the severity increases: Only the second record will be counted as treatment-emergent.
- Both records occur on or after the first dose: If the AE severity on the second record is worse than the severity on the first record, then count both records as treatment-emergent.
- Both records occur on or after the first dose: If the AE one is severe and the other serious then count both records as treatment-emergent.

Of note, when counting the total number of treatment-emergent events, events linked through change in severity will still be counted as separate events.

For events with missing start or stop dates, the following criteria will be used for the purpose of identifying treatment-emergent adverse events:

• If both the start and stop date for a particular event are missing, then the event is considered to have occurred on or after the first dose of study treatment.

Product: Nusinersen	Statistical Analysis Plan
Study: 232SM203	Version: 1.0

- If the start date for a particular event is missing and the stop date/time falls after the first dose date/time, then the event is considered to have occurred on or after the first dose of study treatment.
- If the start time is missing and the start date is same as the first dosing date, then the event is considered to have occurred on or after the first dose of study treatment.
- If it cannot be determined whether or not an event has occurred on or after dosing due to a missing or partial date, then the event will be assumed to have occurred on or after the first dose for the purpose of identifying treatment-emergent adverse events.

Specifically, let AESTDT denote the start date of an adverse event and TRTSTDT be the start date of study treatment. For the purpose of identifying the treatment emergent adverse events, the following algorithm will be used for the imputation of missing or partial date:

- If AESTDT is completely missing or the year is missing, then impute AESTDT to TRTSTDT.
- If, in AESTDT, year is present and month/day are missing and year is equal to the year portion of TRTSTDT, then impute the month/day portion of AESTDT to the month/day portion of TRTSTDT.
- If, in AESTDT, year is present and month/day are missing and year is not equal to the year portion of TRTSTDT, then impute the month/day portion of AESTDT to January 01.
- Consider the situation in AESTDT where year and month are present with only day missing. If the year and month are the same as those for TRTSTDT, then impute day in AESTDT with day in TRTSTDT. Otherwise, impute the day in AESTDT with the first day of the month.

It is important to emphasize that the imputed date will not be used for calculations such as onset and duration of an adverse event.

# iii Concomitant Therapy and Procedure

In order to define concomitant therapies with missing start or stop dates, the following additional criteria will be used:

- If both the start and stop dates of a particular therapy were missing, that therapy is considered concomitant.
- If the start date of a therapy was missing and the stop date of that therapy fell on or after the date of dosing, that therapy is considered concomitant.
- If the start date of a therapy was prior to the date of dosing and the stop date of that therapy was missing and the therapy was listed as continuing, that therapy is considered concomitant.

Product: Nusinersen	Statistical Analysis Plan
Study: 232SM203	Version: 1.0

- If the start date of a therapy was prior to the date of dosing and the stop date of that therapy was missing and the therapy was listed as *not* continuing, that therapy is considered concomitant.
- If the start/stop date of a therapy is partial then where it is not possible to rule out that it was not taken concomitantly it will be considered concomitant.

Denote the end date of medications as CMENDT and the study treatment start date as TRTSTDT. The medication is classified concomitant provided any of the following is NOT true:

- CMENDT is complete and CMENDT is less than TRTSTDT.
- Day of CMENDT missing and year/month of CMENDT is strictly before year-month of TRTSTDT.
- Month of CMENDT is missing and year of CMENDT is strictly before year of TRTSTDT.

#### Product: Nusinersen

Study: 232SM203

# LIST OF ABBREVIATIONS

Abbreviation	Definition
aPTT	activated partial thromboplastin time
ACEND Assessment of Caregiver Experience with Neuromuscular Disease	Assessment of Caregiver Experience with Neuromuscular Disease
AE	Adverse event
ALT	alanine aminotransferase (SGPT)
AST	aspartate aminotransferase (SGOT)
AUC	Area under the curve
BLQ	Below limit of quantification
BUN	blood urea nitrogen
CGIC	Clinical Global Impression of Change
CHOP INTEND	Children's Hospital of Philadelphia Infant Test of Neuromuscular Disorders
CO2	bicarbonate
COVID-19	Coronavirus disease 2019
CSF	Cerebrospinal fluid
CV	Coefficient of variance

Product: Nusinersen
Study: 232SM203

ECG	Electrocardiogram
eCRF	electronic Case report form
GGT	gamma-glutamyl transferase
HFMSE	Hammersmith Functional Motor Scale – Expanded
HINE	Hammersmith Infant Neurological Examination
HRQOL	Health-related quality of life
ІСН	International Council for Harmonization
INR	International normalized ratio
IRT	Interactive response technology
ITT	Intent-to-Treat
LLOQ	lower limit of quantification
LP	Lumbar puncture
MET	Metabolic equivalent task
РТ	prothrombin time
PedsQL	Pediatric Quality of Life Inventory TM
РК	Pharmacokinetic(s)
PPS	Per protocol Set
QoL	Quality-of-life
QTcF	Corrected QT interval using Fridericia's formula

Product: Nusinersen
Study: 232SM203

RULM	Revised Upper Limb Module
SAE	Serious adverse event
SD	Standard deviation
SE	Standard error
SMA	Spinal muscular atrophy
SMN	Survival motor neuron
SMN1	Survival motor neuron 1
SMN2	Survival motor neuron 2
SOC	System Organ Class
ULN	upper limit of normal
WHO	World Health Organization

Product: Nusinersen	Statistical Analysis Plan
Study: 232SM203	Version: 1.0 Final

